5.3 Test of Cure Visit (Visit 3)

The Test of Cure Visit (Visit 3) will occur 21 to 30 days after Visit 1. This is the last visit of the study. The following will be completed:

- Perform physical examination.
- Obtain vital signs after sitting for 5 – 10 minutes ([Section 4.5](#)).
- Measure weight.
- Perform urine pregnancy test.
- Perform pelvic examination including vaginal wall inspection (a naked eye inspection), examination of the cervix, and Investigator's (or designee's) assessment of local site reactions.
- Record subject-assessed local site reactions (e.g., itching, burning/stinging, localized pain).
- Collect a swab sample for central laboratory Nugent's analysis for BV via Gram stain.
- Determine clinical cure of BV by assessing the subject for presence of the following three Amsel's criteria:
 - Resolution of the abnormal vaginal discharge characteristic of BV to a normal physiological discharge; AND
 - Negative "whiff test" after addition of a drop of 10% KOH to vaginal discharge; AND
 - Presence of clue cells at <20% of the total epithelial cells on microscopic examination of the saline wet mount.
- Determine if vaginal pH is <4.7, which is part of the assessment of therapeutic cure (defined as clinical cure, vaginal pH <4.7 and bacteriological cure).
- Record concomitant medications taken since the prior visit along with the indications for the medications.
- Assess and record AEs.

5.4 Early Discontinuation Visit

At any time, if a subject decides to discontinue her participation in the study or is discontinued from the study for any reason, she will be advised to complete Early Termination procedures (i.e., all procedures noted for Visit 3) as an early discontinuation visit. The following will be completed:

- Perform physical examination.
- Obtain vital signs after sitting for 5 - 10 minutes ([Section 4.5](#)).
- Measure weight.

- Perform urine pregnancy test.
- Perform pelvic examination including vaginal wall inspection (a naked eye inspection), examination of the cervix, and local site reaction assessments.
- Record subject-assessed local site reactions (e.g., itching, burning/stinging, localized pain).
- Collect a swab sample for central laboratory Nugent's analysis for BV via Gram stain.
- Clinical test of response of BV will be determined by assessing the subject for presence of these three of the Amsel's criteria:
 - Resolution of the abnormal vaginal discharge; AND
 - Negative "whiff test" after addition of a drop of 10% KOH to vaginal discharge; AND
 - Presence of clue cells at <20% of the total epithelial cells on microscopic examination of the saline wet mount.
- Determine if vaginal pH is <4.7, which is part of the assessment of therapeutic cure (defined as clinical cure, vaginal pH <4.7 and bacteriological cure).
- Study medication will be returned by the subject, including any unused applicators (unless previously collected).
- Record concomitant medications taken since the prior visit along with the indications for the medications.
- Assess and record AEs.

5.5 Unscheduled Visit

The investigator may see the subject for an unscheduled visit to manage or assess AEs.

At this visit, the investigator or designee will:

- Assess AEs and local site reactions since the last visit; AEs and local site reactions will be recorded.
- Record any changes in the subject's concomitant medications.
- Confirm the next appointment (to be done at a time the subject does not expect to be menstruating).

5.6 Schedule of Assessments

The schedule of assessments is provided in [Table 3](#).

Table 3 Schedule of Assessments

Visit	Visit 1	Visit 2	Visit 3	
Visit Name	Entry Visit	Post-Treatment Assessment	Test of Cure	Early Termination ^a
Study Day(s)	1	7 to 14 days	21 to 30	
Informed consent	X			
Inclusion/exclusion criteria	X			
Demographics	X			
Medical and gynecological history	X			
Physical examination	X		X	X
Pelvic examination	X	X	X	X
Height	X			
Weight	X		X	X
Vital signs (after sitting for 5 - 10 mins)	X	X	X	X
Concomitant medications	X	X	X	X
Randomization ^b	X			
Dispense study medication ^c and dosing instructions	X			
Collect study medication		X		X ^d
Assessment of local site reactions		X	X	X
Adverse events	X	X	X	X
Urine pregnancy test	X	X	X	X
Urine drug screen	X			
Amsel's criteria evaluations:				
-Assessment of vaginal discharge	X	X	X	X
-KOH Whiff Test	X	X	X	X
-Saline Wet Mount	X	X	X	X
-pH	X	X	X	X
Collection of samples for Nugent's score based on Gram stain (send to central laboratory)	X		X	X
Collection of samples for STI assessment ^e (send to central laboratory)				
	X			

- a. At any time a subject decides to discontinue her participation in the study or is discontinued from the study for any other reason, she will be advised to complete the Early Termination procedures.
- b. Randomization to occur if the results of the full set of Amsel's criteria are positive.
- c. Study medication will be dispensed at Visit 1. The subject will be instructed to self-administer study medication intravaginally once daily at bedtime for 5 consecutive days.
- d. Unless collected at previous visit.
- e. Central laboratory analysis for *Chlamydia trachomatis* and *Neisseria gonorrhoeae*.

6 END OF STUDY CRITERIA

At the end of each subject's participation in the study, the investigator will complete an End of Study form for all completed and discontinued subjects.

6.1 Completion of the Study

Subjects who complete the 5-day treatment and all of the evaluations at the Assessment of Clinical Cure Visit (Visit 3) will be considered to have completed the study.

6.2 Subject Discontinuation

A subject may be withdrawn from the study prior to completion for any of the following reasons:

- AEs
- Abnormal laboratory values
- Death
- Lack of efficacy
- Lost to follow-up
- Noncompliance with study drug
- Physician decision
- Pregnancy (if applicable)
- Protocol deviation
- Study terminated by Sponsor
- Withdrawal by subject; NOTE: if the subject decides to withdraw from the study due to an AE then it should be classified as withdrawal due to an AE.
- Other (e.g., any reason that may affect the outcome of the study or safety of subjects)

If a subject withdraws prematurely for any reason, the site should make every effort to have the subject return for her next scheduled visit to perform all required visit activities and to collect and reconcile all test article. If the subject is discontinued prior to the Assessment of Clinical Cure Visit (Visit 3; Day 21 to 30), the site should complete the End of Study eCRFs during the last visit that the subject will complete. Subjects who withdraw prematurely will not be replaced. When a subject is withdrawn from the study for a treatment-related AE (i.e., as defined in [Section 8.1.2](#)), when possible, the subject should be followed until resolution or stabilization of the AE. If a subject is discontinued from the study due to pregnancy, the pregnancy and its outcome should be followed (see [Section 8.1.5](#)).

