3.4 Withdrawal of Subjects

Subjects may withdraw from the study at any time or be withdrawn from the study at the discretion of the investigator should any untoward effects occur. In addition, a subject may be withdrawn by the investigator or the sponsor if she deviated from the protocol or for other safety reasons.

Subjects withdrawing from the study will not be replaced, regardless of the reason for discontinuation. All reasonable efforts should be made to contact the subject if she decides to discontinue study treatment.

The procedures noted in the Schedule of Assessments ([Table 3](#)) should be performed for the Early Termination Visit, whenever it occurs. A subject will be considered to have completed the study after completing the Test of Cure Visit (Visit 3). If a subject is discontinued at any time after entering the study, the investigator will make every effort to see the subject and complete the early discontinuation assessments as shown in Schedule of Assessments ([Table 3](#)) and [Section 5.4](#).

A termination electronic case report form (eCRF) page should be included for each subject who receives study medication, whether or not the subject completes the study. The reason for any early discontinuation should be indicated on the form. The primary reason for a subject withdrawing prematurely should be selected from the list provided in [Section 6.2](#).

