Subjects in the mITT population who discontinue early from the study, and do not have an assessment of Clinical Cure or Bacteriological Cure will be included in the mITT population as treatment failures. These subjects without actual outcomes, but are classified as treatment failures will not be included in the PP analysis population.

sm **W W I** **W**

Subject demographics and pre-treatment characteristics will be summarized for the ITT analysis population, and some of these summaries may also be done for other populations when deemed important.

sharp

A summary of demographics and subject characteristics will be created for the ITT, Safety, mITT, and PP populations, and include age, race, ethnicity, height, weight, and body mass index (BMI) at the study entry visit with:

- 6-number statistics (number of non-missing observations, mean, median, SD, minimum, and maximum) for age, height, baseline weight, baseline BMI (to be calculated, see formula in [Section 3.8.4](#)) by treatment group and for all subjects.
- Age will be calculated (with the INTCK function in SAS®) using the study entry visit date and the date of birth. Subject age (years) will also be categorized as 18-20, 21-30, 31-40, 41-50, 51+, and then summarized categorically along with race, ethnicity.
- BMI at the study entry visit will also be categorized as: Underweight (< 18.5), Normal (18.5 – 24.9), Overweight (25.0 – 29.9), and Obese (≥ 30.0). The number and percentage of subjects in each of these categories will be presented by treatment group and for all subjects.

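### Women may be withdrawn from the study for missed doses or a deviation, and two conflicting exit instructions then decide whether their mITT outcome is a Day 21-30 Test of Cure or an earlier exam

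*Protocol*

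**What the plan says.** **Withdrawal.** Protocol 6.2 opens its list with "A subject may be withdrawn from the study prior to completion for any of the following reasons" and includes "Noncompliance with study drug" and protocol deviation. Protocol 3.4 adds that "a subject may be withdrawn by the investigator or the sponsor if she deviated from the protocol or for other safety reasons". Both are permissive. Neither says whether a woman withdrawn on these grounds is still seen at Visit 3.

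**Exit procedure.** Protocol 6.2: "the site should make every effort to have the subject return for her next scheduled visit to perform all required visit activities". Protocol 5.4: "she will be advised to complete Early Termination procedures (i.e., all procedures noted for Visit 3) as an early discontinuation visit". Protocol 3.4 and Table 3 agree with 5.4 and place no limit on when that visit occurs.

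**Completer.** Protocol 3.4: "A subject will be considered to have completed the study after completing the Test of Cure Visit (Visit 3"). Protocol 6.1 asks for more: "Subjects who complete the 5-day treatment and all of the evaluations at the Assessment of Clinical Cure Visit (Visit 3").

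**Analysis.** For the mITT superiority tests, SAP 3.7.1 takes Visit 3 for completers, the Early Termination exam for discontinued women, and the Visit 2 exam if neither exists. SAP 3.4 says that women who discontinue early and "do not have an assessment of Clinical Cure or Bacteriological Cure will be included in the mITT population as treatment failures".

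**The concern.** Treatment lasts five nights and the endpoint is read at least 21 days after randomization. Missing doses is therefore no reason to miss the Test of Cure, and Visit 3 is already scheduled for every woman. The protocol can separate the two ideas: section 3.5.8 stops study drug after emergency unblinding without mentioning study withdrawal, and Appendix 2 tells a woman who misses a dose to carry on the next evening.

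The mITT comparison with vehicle is the assay-sensitivity test, and its endpoint is defined at Visit 3. If a discretionary withdrawal, followed by the site's choice between two exit sections, decides whether a woman contributes a true Test of Cure, an exam one to three weeks too early, or an imputed failure, the endpoint no longer has one meaning across women or sites. The two secondary cure endpoints are exposed as well, because the Gram stain is not scheduled at Visit 2.

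**Working it through.** **1. The exit instructions applied to the same woman**

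| Situation | Following Protocol 6.2 | Following Protocol 5.4, 3.4 and Table 3 |
|---|---|---|
| Non-compliance found at Visit 2 | Next scheduled visit is Visit 3, so the Day 21-30 outcome is kept | Early Termination exam; if done then, at about Day 7-14 |
| Leaves before Visit 2 | Visit 2 and its activities, no Gram stain | Full Visit 3 set with Gram stain, but early |

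The first row is the likelier one: study drug is collected and dosing verified at Visit 2 (Protocol 5.2, Table 3). An exam there falls 21 - 14 = 7 to 21 - 7 = 14 days before the earliest Test of Cure, and up to 30 - 7 = 23 days before the latest.

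**2. What the SAP does next.** In the first row, SAP 3.7.1 uses a true Test of Cure under 6.2 and the early exam under 5.4. In the second row under 6.2, the Visit 2 exam is carried forward for clinical cure; there is no Nugent score, so bacteriological and therapeutic cure have no full assessment. The failure rule in SAP 3.4 is worded with an *or* between the two cures, where Protocol 9.2 has *and*, so on one reading a missing Nugent score alone triggers it.

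**3. The plan's sample size.** Inputs (Protocol 9.1): 36% against 20%, 12.4% not in mITT, 90% power; two-sided 0.05 (Protocol 9.6.1). The continuity-corrected two-proportion formula gives 176 per arm; 176 / 0.876 = 200.9, so 201; 3 x 201 = 603, as stated. At 95% power the same formula gives 215; 215 / 0.876 = 245.4, so 246; 3 x 246 = 738, which equals the planned total. Expected mITT is 246 x 0.876 = 215.5, taken as 215 per arm.

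**4. Outcomes lost and scored as failures, equally in all arms.** The rate f is an assumption. Rates become 0.36(1 - f) and 0.20(1 - f), and the difference 0.16(1 - f).

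- f = 2%: about 4 women per arm (0.02 x 215.5 = 4.3); difference 0.1568, a loss of 0.3 points.
- f = 8%: about 17 women per arm (0.08 x 215.5 = 17.2); difference 0.1472, a loss of 1.3 points.

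Power for one active-vehicle comparison is Φ{[d - 1.96 √(2p̄(1 - p̄)/n)] / √[(p₁(1 - p₁) + p₂(1 - p₂))/n]}. With n = 215 and no loss: (0.16 - 1.96 x 0.0433) / 0.0426 = 1.76, or 96.1%. At f = 2, 5, 8 and 10% it is 95.6, 94.9, 94.0 and 93.3%.

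Both actives must beat vehicle. Simulating three arms of 215 with both actives at 36%, joint power is 93.2% with no loss and 89.7% at f = 8%. With one active at 40% it is 95.9% and 93.6%.

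**5. Early exam substituted in 10% of women** (assumed early cure rates; each arm is 0.9 x its Visit 3 rate + 0.1 x its early rate)

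| Early cure, active / vehicle | Difference | Power, one comparison |
|---|---|---|
| 50% / 20% | 0.374 - 0.200 = 0.174 | 98.1% |
| 60% / 25% | 0.384 - 0.205 = 0.179 | 98.4% |
| 20% / 20% | 0.344 - 0.200 = 0.144 | 92.1% |

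**6. Loss in the vehicle arm only, scored as failure.** The difference is 0.36 - 0.20(1 - f): 0.17, 0.18 and 0.20 at f = 5, 10 and 20%, against 0.16 with full data.

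Steps 4 to 6 show that the error can go either way.

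**The case against.** The case against is substantial, and most of it limits the point rather than removing it.

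- **A reader might infer that the plan removes non-compliant women.** It does not. The wording is permissive, and Protocol 3.4 also uses the 6.2 list as the source of recorded withdrawal reasons; it includes death and loss to follow-up, which are not removal decisions.
- **A reader might infer that the 6.2 sentence costs the Test of Cure.** For a woman found non-compliant at Visit 2 it preserves it; 5.4 is what substitutes an earlier exam. This stands, and it makes the conflict sharper.
- **The 6.2 sentence could be about when to bring her back, with 5.4 giving the content.** That is possible, but the text does not say so, and for a woman past Visit 2 the two still give different dates. Any worry about a missed physical examination is answered by Protocol 7.2, which has safety assessments repeated at withdrawal.
- **A reader might infer that these women drop out of mITT or all become failures.** They stay in, and SAP 3.7.1 usually supplies an earlier exam for clinical cure. The failure rule matters mainly where no exam exists, and for the secondary endpoints, which have no planned test.
- **The completer mismatch defines no analysis population.** Correct. It affects disposition counts and the completer wording in SAP 3.7.1; a woman who attends Visit 3 has her Visit 3 data either way.
- **Equivalence is barely touched.** It is judged in Per Protocol, which already excludes women with fewer than 5 doses or without an in-window Visit 3, apart from lack-of-efficacy discontinuations after at least 3 doses. This stands, and it also means that withdrawal is not needed to protect that analysis.

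**Conclusion.** The point holds in a limited form. The documents allow withdrawal from follow-up for reasons that do not prevent a Visit 3 assessment, give two exit instructions that lead to different data for the same woman, and pass the difference into the mITT superiority test through SAP 3.7.1.

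The size is unknown, because the documents give neither a withdrawal rate for these reasons nor an early cure rate; 2-8% and the early rates above are assumptions. Within 2-8% equal loss the effect on the difference is about a point at most, and each comparison keeps more than 90% power. Joint power for both comparisons reaches about 90% only at the top of that range with both actives at 36%. A reading that the trial is materially underpowered is not supported. What remains is an avoidable mixed-time outcome, with bias that may raise or lower the active-vehicle difference depending on exit route and arm. It should be corrected because the correction is cheap.

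**What to change.** Reconcile Protocol 3.4, 5.4, 6.1 and 6.2 with each other and with SAP 3.4 and 3.7.1:

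1. State that a woman who misses doses or deviates, and has not withdrawn consent, is still asked to attend Visit 3 in its window. Record the non-compliance or deviation as data.
2. Give one exit procedure for women who do leave, worded identically wherever it appears.
3. Use one definition of completer throughout.
4. In the SAP, say which rule applies, the failure rule or the carried-forward exam, when only one of the two cure assessments is missing.

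Safety-related withdrawal, dosing rules and the Per Protocol exclusions need no change for this and remain the sponsor's to settle. The cost is protocol and SAP wording plus site training. No visit or procedure is added; the downside is a few more Visit 3 attendances to chase.

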6.3 Study Termination

The study may be terminated by the Sponsor. If, in the opinion of the investigator, clinical observations made during the study suggest that it may be unwise to continue, he or she may discontinue his or her participation in the study.

If an investigator decides to terminate his or her participation, a written statement fully documenting the reasons for this action will be submitted to the Sponsor by the investigator within five working days.

In the event that the Sponsor chooses to discontinue or terminate the study, appropriate notification will be given to the investigator.

7 EVALUATIONS

7.1 Efficacy Parameters

The primary efficacy endpoint (Clinical Cure) is the resolution of the following three abnormal BV signs included in Amsel's criteria: return to normal physiological vaginal discharge as determined by the investigator, negative whiff test, and the presence of clue cells at <20% of the total epithelial cells on microscopic examination of the saline wet mount.

The supportive secondary efficacy endpoints are the Bacteriological Cure and the Therapeutic Cure. The bacteriological cure is defined as Nugent's score <4 (via Gram stain central laboratory analysis). A Nugent score ≥ 4 is considered abnormal and represents an imbalance in vaginal flora that permits BV to manifest (Nugent 1991). Subjects who are responders are expected to achieve a normal Nugent score (i.e., 0 to 3) following treatment.

Therapeutic cure is defined as having achieved clinical cure, vaginal pH of <4.7, and bacteriological cure (i.e., Nugent score of < 4 at Visit 3).

7.2 Safety Evaluation

Each subject's health status will be monitored carefully throughout the study. Baseline data collected will consist of the medical and gynecological history and physical examination findings, including pelvic examinations (to include STI screening for Chlamydia and gonorrhea).

Vital signs include oral temperature, sitting blood pressure, heart rate, and respiratory rate. Blood pressure will be collected after sitting for 5 to 10 minutes and should be taken from the same arm at each visit.

Weight will be recorded at the Entry Visit (Visit 1) and the Assessment of Continued Clinical Cure Visit (Visit 3).

Subjects who withdraw from the study will have all safety assessments repeated except for urine drug and STI testing, if the subject allows.

At every visit or contact, subjects will be questioned about how they have been feeling and any symptoms they have experienced. Interviews with subjects will include a review of any AE reported in order to obtain as much information as possible (e.g., onset date, duration, intensity). The AEs will be recorded at each visit in the medical records and the eCRF. See [Section 8.1](#) for AE definitions and criteria, including assessments for intensity and relatedness. In addition, local site reactions based on investigator examination and subject self-report will be assessed at Visits 2 and 3.

The principal investigator (or designated medical designee) will review each AE, assess severity and causality and will report it in accordance with established procedures (see [Section 8.1.1.4](#)).

There will be strict adherence to SAE reporting (see [Section 8.1.3.2](#)).

7.3 Appropriateness of Measurements

As stated in [Section 3.2](#), the study design relied heavily on the recommendations provided in FDA draft guidances.

8 SAFETY

The primary method of assessing safety will be collection and analysis of AEs. AEs and SAEs will be carefully monitored throughout this study.

8.1 Adverse Events and Serious Adverse Events

8.1.1 Definitions and Criteria

8.1.1.1 Adverse Events (AEs)

An AE is any untoward medical occurrence associated with the use of a drug in humans, whether or not considered related. An AE can therefore be any unfavorable and unintended sign (including an abnormal laboratory finding), symptom, or disease temporally associated with the use of a medicinal product.

Suspected adverse reaction is any AE for which there is a reasonable possibility that the drug caused the AE. "Reasonable possibility" means there is evidence to suggest a causal relationship between the drug and the AE. A suspected adverse reaction implies a lesser degree of certainty about causality than adverse reaction, which means any AE caused by a drug.

An adverse reaction is any AE caused by a drug. Adverse reactions are a subset of all suspected adverse reactions for which there is reason to conclude that the drug caused the event. For the purposes of prescription drug labeling, the term adverse reaction is defined to mean "an undesirable effect, reasonably associated with the use of a drug that may occur as part of the pharmacological action or may be unpredictable in its occurrence. This definition does not include all AEs observed during use of a drug, only those AEs for which there is some basis to believe there is a causal relationship between the drug and the occurrence of the AE".

An AE or suspected adverse reaction is considered "unexpected" if it is not listed in the RLD package insert or is not listed at the specificity or severity that has been observed. For example, under this definition, hepatic necrosis would be unexpected (by virtue of greater severity) if the RLD package insert referred only to elevated hepatic enzymes or hepatitis. Similarly, cerebral thromboembolism and cerebral vasculitis would be unexpected (by virtue of greater specificity) if the RLD package insert listed only cerebral vascular accidents. "Unexpected," as used in this definition, also refers to AEs or suspected adverse reactions that are mentioned in the RLD package insert as occurring with a class of drugs or as anticipated from the pharmacological properties of the drug, but are not specifically mentioned as occurring with the particular drug under investigation.

Timely and complete reporting of all AEs assists [REDACTED] in identifying any untoward medical occurrence, thereby allowing:

- 1) protection of the safety of study subjects;
- 2) a greater understanding of the overall safety profile of the test article;
- 3) recognition of dose-related test article toxicity;
- 4) appropriate modification of study protocols;
- 5) improvements in study design or procedures; and

6) adherence to worldwide regulatory requirements.

Any adverse change from the study participant's baseline condition that occurs following the first administration of study product is an AE. This includes the occurrence of a new AE or the worsening of a baseline condition, whether or not considered related to the study product. AEs include but are not limited to: adverse changes in the general condition of the study participant; signs and symptoms noted by the study participant or her caregiver; concomitant disease with onset or increased severity after the start of study product administration and clinically meaningful adverse changes in laboratory safety parameters occurring after the start of study product administration. Day-to-day fluctuations in pre-existing conditions that represent a clinically significant change in the participant's status should be reported as AEs.

